2.1.4.1 Hypoglycemia

Hypoglycemia will be identified as events recorded on the dedicated e-CRF “Hypoglycemic event information” page, and will be categorized as follows (see study protocol for further details):

Severe hypoglycemia

Severe hypoglycemia is an event requiring assistance of another person to actively administer carbohydrate, glucagon, intravenous glucose or other resuscitative actions. These episodes may be associated with sufficient neuroglycopenia to induce seizure, unconsciousness or coma.

Self-monitored plasma glucose values may not be available, but neurological recovery attributable to the restoration of plasma glucose to normal is considered sufficient evidence that the event was induced by a low plasma glucose concentration.

Severe hypoglycemia is identified in e-CRF “Hypoglycemic Event Information” page as those documented as,

1. To the question “Countermeasure Administration”, ticked the option “Subject was Not Capable of Treating Self and Required Assistance”, and
2. To the question “Were Symptoms Present”, ticked “Yes”.

Documented symptomatic hypoglycemia

Documented symptomatic hypoglycemia is an event during which typical symptoms of hypoglycemia accompanied by a measured plasma glucose concentration of ≤ 3.9 mmol/L (≤ 70 mg/dL).

Clinical symptoms that are considered to result from a hypoglycemic episode include increased sweating, nervousness, asthenia/weakness, tremor, dizziness, increased appetite, palpitations, headache, sleep disorder, confusion, seizures, unconsciousness, or coma.

Documented symptomatic hypoglycemia is identified in e-CRF “Hypoglycemic Event Information” page as those documented as,

1. To the question “Countermeasure Administration”, NOT ticked the option “Subject was Not Capable of Treating Self and Required Assistance”, and
2. To the question “Were Symptoms Present”, ticked “Yes”, and
3. With a plasma glucose value before countermeasure ≤ 3.9 mmol/L (≤ 70 mg/dL).

Asymptomatic hypoglycemia

Asymptomatic hypoglycemia is an event not accompanied by typical symptoms of hypoglycemia but with a measured plasma glucose concentration ≤ 3.9 mmol/L (≤ 70 mg/dL).

Asymptomatic hypoglycemia is identified in e-CRF “Hypoglycemic Event Information” page as those documented as,

1. To the question “Countermeasure Administration”, NOT ticked the option “Subject was Not Capable of Treating Self and Required Assistance”, and
2. To the question “Were Symptoms Present”, ticked “No”, and
3. With a plasma glucose value before countermeasure ≤ 3.9 mmol/L (≤ 70 mg/dL).

Probable symptomatic hypoglycemia

Probable symptomatic hypoglycemia is an event during which symptoms of hypoglycemia are not accompanied by a plasma glucose determination, (but that was presumably caused by a plasma glucose concentration ≤ 3.9 mmol/L [≤ 70 mg/dL]), ie, symptoms treated with oral carbohydrate without a test of plasma glucose.

Probable symptomatic hypoglycemia is identified in e-CRF “Hypoglycemic Event Information” page as those documented as,

1. To the question “Countermeasure Administration”, NOT ticked the option “Subject was Not Capable of Treating Self and Required Assistance”, and
2. To the question “Were Symptoms Present”, ticked “Yes”, and
3. With no plasma glucose value before countermeasure, and
4. To the question “Did this countermeasure lead a significant improvement or prompt recovery”, ticked “Yes”.

Relative hypoglycemia

Relative hypoglycemia, recently termed “pseudo-hypoglycemia”, is an event during which the patient reports typical symptoms of hypoglycemia, and interprets the symptoms as indicative of hypoglycemia, but with a measured plasma glucose concentration > 3.9 mmol/L (> 70 mg/dL).

Relative hypoglycemia is identified in e-CRF “Hypoglycemic Event Information” page as those documented as,

1. To the question “Countermeasure Administration”, NOT ticked the option “Subject was Not Capable of Treating Self and Required Assistance”, and
2. To the question “Were Symptoms Present”, ticked “Yes”, and
3. With a plasma glucose value before countermeasure > 3.9 mmol/L (> 70 mg/dL).

In addition of the threshold of ≤ 3.9 mmol/L (≤ 70 mg/dL), hypoglycemia episodes with plasma glucose of < 3.0 mmol/L (< 54 mg/dL) will be analyzed separately.

Any hypoglycemic event fulfilling the criteria of a SAE or leading to unconsciousness, coma, or seizure will also be recorded as a SAE (see [Section 2.1.4.2](#)).

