### Severe hypoglycemia

Severe hypoglycemia is an event requiring assistance of another person to actively administer carbohydrate, glucagon, intravenous glucose, or other resuscitative actions. These episodes may be associated with sufficient neuroglycopenia to induce seizure, unconsciousness or coma. Self-monitored blood glucose values may not be available, but neurological recovery attributable to the restoration of plasma glucose to normal is considered sufficient evidence that the event was induced by a low plasma glucose concentration.

**Note:** “Requiring assistance of another person” means that the patient could not help himself or herself to treat the hypoglycemia. Assisting a patient out of kindness, when assistance is not required, should not be considered a “requires assistance” incident.

Any hypoglycemic event which leads to unconsciousness, coma, or seizure should also be reported as an **SAE**.

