Sustained eGFR <15 mL/min/1.73 m ²	(2) For eGFR <15 mL/min/1.73 m ² , (2a) confirmed eGFR <15 mL/min/1.73 m ² for ≥30 days with no reversible cause as recorded in eCRF "eGFR decrease", OR (2b) positively adjudicated by CEC: Yes to the question "Does the subject meet the criteria of CKD progression".
Chronic dialysis	(3) For dialysis, (3a) dialysis lasted for ≥90 days (eg, end date - start date+ 1 ≥90) as recorded in eCRF "Renal Event - Dialysis", OR (3b) positively adjudicated by CEC: Yes to the question ". Does the subject meet the criteria for ESRD".
Renal transplant ^a	(4) "Renal transplant" captured in eCRF "Other procedure form", where adjudication is not required. PTs of Renal transplant (10038533), Renal and pancreas transplant (10052278), Renal and liver transplant (10052279) based on MedDRA v21.1.
Renal death	(5) Renal death as positively adjudicated by CEC: "Death - Non-Cardiovascular (Renal)" as the primary cause of death
EOSI not adjudicated^a	
Severe hypoglycemia	Algorithm specified in Section 2.1.4.1 based on eCRF "Hypoglycemic Events"
Genital mycotic infections	PTs in Appendix C
Urinary tract infections	PTs in Appendix C
Clinically relevant volume depletion and events related/possibly related to volume depletion	PTs in Appendix C
Diarrhea	Narrow search on "Noninfectious diarrhoea (SMQ)" [20000218] plus the following PTs (MedDRA v21.1): Gastroenteritis (10017888), Antidiarrhoeal supportive care (10055660), Enteritis (10014866), Enteritis leukopenic (10014877), Enterocolitis (10014893), Enterocolitis haemorrhagic (10014896)
Pancreatitis	PTs in Appendix C
Venous thrombotic events	PTs in Appendix C
Malignancies of special interest	Breast cancer: Narrow search on "Breast neoplasms, malignant and unspecified (SMQ)" [20000149] Prostate cancer: Narrow search on "Prostate neoplasms, malignant and unspecified (SMQ)" [20000152] Leydig-cell cancer: PTs of Leydig cell tumour of the testis (10024407) and Ovarian Sertoli-Leydig cell tumour (10073270) based on MedDRA v21.1 Thyroid cancer: PTs in Appendix C Renal cell cancer: PTs in Appendix C Pancreatic cancer: PTs in Appendix C Bladder cancer: PTs in Appendix C
EOSI AE leading to an amputation	
AE leading to an amputation	"AE Correction" as the reason for amputation in eCRF "Other Procedures related to amputation"
AE potentially leading to an amputation ^{a,b}	PTs in Appendix C

AE Grouping	Criteria

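### The SAP's e-CRF rule for severe hypoglycemia adds a symptom condition that its own definition lacks, leaving some assisted events in no category

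*SAP*

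**What the plan says.** SAP 2.1.4.1 gives a text definition: "Severe hypoglycemia is an event requiring assistance of another person to actively administer carbohydrate, glucagon, intravenous glucose or other resuscitative actions". It then describes a possible feature of such events, not a requirement: "These episodes may be associated with sufficient neuroglycopenia to induce seizure, unconsciousness or coma". Protocol 10.6.1 uses the same definition: "Severe hypoglycemia is an event requiring assistance of another person to actively administer carbohydrate, glucagon, intravenous glucose, or other resuscitative actions".

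The SAP then turns the definition into an e-CRF rule with two conditions joined by 'and'. On the countermeasure question, the site has "ticked the option “Subject was Not Capable of Treating Self and Required Assistance”, and" the second condition is "To the question “Were Symptoms Present”, ticked “Yes".

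The rules for documented symptomatic, asymptomatic, probable symptomatic and relative hypoglycemia all open with the opposite condition on the countermeasure question: "NOT ticked the option “Subject was Not Capable of Treating Self and Required Assistance".

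Table 3 in SAP 2.1.4.2 lists severe hypoglycemia among the events of special interest that are not adjudicated. Its identification criterion is "Algorithm specified in Section 2.1.4.1 based on eCRF" the hypoglycemia form. SAP 2.4.5.1 uses the resulting category for the severe counts and for both types of incidence rate. It also enters the subgroup tables and the Kaplan-Meier curve of time to first severe or documented symptomatic event.

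**The concern.** The programmed rule is narrower than the definition it is meant to implement. An event that the site records as one the patient could not self-treat meets the definition. If the symptoms question says No or is blank, the rule does not call it severe, and no other category can take it.

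Severe hypoglycemia is a named event of special interest in a CKD population where insulin is allowed both as background and as rescue therapy. It is identified by this rule with no adjudication behind it, so a committee would not catch a misclassified event. SAP 2.5.3 gives no default for a missing symptom answer. Elsewhere that section resolves ambiguity towards inclusion: a missing causality assessment is treated as related, and an unclear onset date as treatment-emergent. Here the silent default is exclusion.

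**Working it through.** No sample size, power or rate calculation applies. The check is whether the five rules cover every possible form entry.

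**Inputs (SAP 2.1.4.1).** The rules use four e-CRF fields:
- assistance option: ticked or not (2 values)
- symptoms present: Yes, No or blank (3)
- plasma glucose before countermeasure: at or below 3.9 mmol/L, above 3.9 mmol/L, or none (3)
- prompt recovery: Yes, or No/blank (2)

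This gives 2 × 3 × 3 × 2 = 36 combinations, of which 3 × 3 × 2 = 18 have assistance ticked.

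**Rules as written**

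| Assistance ticked, symptoms | Combinations | Category |
|---|---|---|
| Yes | 3 × 2 = 6 | Severe |
| No | 3 × 2 = 6 | None |
| Blank | 3 × 2 = 6 | None |

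So 6 + 6 = 12 of the 18 assisted combinations fall in no category. No combination falls in two.

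**Symptom condition removed from the severe rule.** All 18 assisted combinations are severe, none is unclassified, and there is still no overlap.

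**Unassisted entries.** The other four rules cover 2 (documented) + 2 (asymptomatic) + 1 (probable) + 2 (relative) = 7 of 18. The remaining 11 are unclassified under either version. They do not touch the severe count. Total unclassified goes from 12 + 11 = 23 to 11.

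These are counts of form entries, not of expected patients.

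**Where an unclassified assisted event still appears**
- Any hypoglycemia: yes. SAP 2.1.4.1 identifies hypoglycemia by entry on the dedicated page, whatever the category.
- Listing in SAP 2.4.5.1: yes, but with no category flag.
- SAE tables: yes, if it meets SAE criteria or led to unconsciousness, coma or seizure (SAP 2.1.4.1).
- Severe event of special interest, severe counts and rates, severe-or-documented subgroup tables, and the Kaplan-Meier curve: no.

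**The case against.** The best defence is that a true severe event nearly always carries a Yes. The footnote to protocol Figure 1 ties the need for help to acute neurological impairment, and the SAP's symptom list includes confusion, seizures, unconsciousness and coma. A blank is first a matter for data queries, which protocol 13.4 provides for. This stands, and it is why the practical effect is probably small. A reader might infer that a patient found unresponsive would be lost. On the SAP's own symptom list that patient should be ticked Yes and counted, so only a missing or wrong tick loses the event.

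A second defence is that the symptom tick screens out false entries. The severe rule has no glucose or recovery criterion, so without the tick an assisted event with no supporting evidence counts as severe. Of the 12 combinations that would become severe, 8 have glucose above 3.9 mmol/L or no glucose value (2 symptom answers × 2 glucose states × 2 recovery answers). This is a real but limited cost. The present rule already accepts 4 of its 6 severe combinations without a low glucose value, and the definition allows for a missing one. The form option itself requires that the patient was incapable of self-treatment, which addresses the protocol's warning about help given out of kindness. As a screen, the condition also fails on its own terms: it does not move doubtful events to another category but leaves them in none.

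Third, Figure 1 is not shown in the text available, so whether it has a symptom branch cannot be checked. The mismatch between the SAP's text definition and its own rule does not depend on the figure.

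**Conclusion.** The point holds as an internal contradiction. The rule requires something the definition does not, and assisted events marked No or blank for symptoms have no category. The loss is confined to the severe event of special interest and the analyses built on the severe flag.

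Three stronger readings are not supported:
- **That these events vanish from safety reporting.** They remain in any hypoglycemia, in the listing and, where criteria are met, among SAEs.
- **That the true severe rate is necessarily understated.** Compared with the assistance tick the rule can only remove events, but a mis-ticked assistance box is possible too.
- **That the loss has a known size.** A reader could assume that 1–3% of 260 patients per arm have a severe event, which is 2.6 to 7.8 patients, and infer that each lost patient lowers an arm's count by 1/7.8 = 13% to 1/2.6 = 38%. The documents give no event rate. That arithmetic shows only that small counts are sensitive to one patient. It says nothing about how often an assisted event lacks a Yes.

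The number affected cannot be computed and may be zero. The safety analyses are descriptive, so no hypothesis test is at stake. The case for correction rests on the definition, on the lack of adjudication and on the very low cost.

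**What to change.** - In SAP 2.1.4.1, delete the symptom condition from the severe rule, so that the assistance tick alone classifies an event as severe, as in the text definition and protocol 10.6.1. Table 3 follows without further edits because it refers to that section.
- Before the final database lock, query every assisted event with symptoms No or blank.
- SAP 1.6 records that the first-step analysis has already been reported for top-line results. Log this change with its date and reason, and show the severe count by arm under both rules.

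The cost is one SAP line, one programming condition, a short query list and one extra table row, all on data already collected. The downside is that a few mis-ticked assisted events without symptom or glucose support may be counted as severe. The queries and the two-rule display make those visible.

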2.1.4.2 Adverse events variables

Adverse event observation period

- Pretreatment adverse events are adverse events that developed or worsened or became serious from the signed informed consent date up to first administration of double-blind IMP.
- Treatment-emergent adverse events are adverse events that developed or worsened or became serious during the treatment-emergent adverse event period.
- Posttreatment adverse events are adverse events that developed or worsened or became serious during the posttreatment period.

All adverse events (including SAE, AESI and EOSI) will be coded to a LLT, PT, HLT, HLG, and associated SOC using the version of MedDRA currently in effect at Covance at the time of database lock.

The occurrence of adverse events (including SAE, AESI and EOSI) will be recorded from the time of signed informed consent until the end of the study (see [Section 2.1.4](#)) or the resolution/stabilization of all SAE, AESI and EOSI.

AESI include:

- Pregnancy.
- Symptomatic overdose with IMP/NIMP.
- Alanine aminotransferase (ALT) increase >3 times upper limit of normal (ULN).

EOSI include:

- MACE (CV death, MI, or stroke) and other specific CV events (eg, heart failure requiring hospitalization).
- Severe hypoglycemia (see [Section 2.1.4.1](#)).
- Genital mycotic infections (to include vulvovaginal candidiasis in females and candida balanitis in males).
- Urinary tract infections.
- Clinically relevant volume depletion and events related/possibly related to volume depletion.
- Diarrhea.
- Pancreatitis.
- Bone fractures.
- Venous thrombotic events, to include deep venous thrombosis and thromboembolism (to include pulmonary embolism).
- Diabetic ketoacidosis (DKA).

- Renal events, to include 50% decline in eGFR, end-stage kidney disease, renal death.
- Malignancies of special interest (breast, bladder, renal cell, Leydig cell, pancreatic, prostate, and thyroid cancer).
- AE leading to an amputation.

The Clinical Endpoint Committee (CEC) will, in a blinded manner review and adjudicate all deaths, myocardial infarction, stroke, unstable angina requiring hospitalization, and heart failure requiring hospitalization, selected renal events, bone fracture, and DKA.

Two independent committees will review safety events that require ongoing monitoring to ensure timing protocol amendments in case a safety signal is identified. These events are: 1) potential cases of drug-induced liver injury (DILI), and 2) cases of amputations. The two committees will review the cases in a treatment-blinded manner and will present their assessment to the DMC.

AESI and EOSI will be identified based on criteria in [Table 3](#).

Table 3 - Criteria for AESI and EOSI

AE Grouping	Criteria
AESI	
Pregnancy	eCRF "Pregnancy"
Symptomatic overdose with IMP/NIMP	"Overdose of IMP" or "Overdose of NIMP" checked and "Symptomatic overdose" checked in eCRF "Overdose"
ALT increase >3 X ULN	eCRF "ALT increase"
EOSI adjudicated	
Cardiovascular death	Positively adjudicated by CEC: "Cardiovascular" or "Undetermined" as the primary cause of death
Myocardial infarction, Unstable Angina requiring hospitalization	Positively adjudicated by CEC: Yes to the question "Does the event meet the definition of an MI for this study?", or Yes to the question "If event is not an MI, does the event meet the definition of an UA Requiring admission to hospital or emergency room, for this study?"
Stroke	Positively adjudicated by CEC: Yes to the question "Does the event meet the definition of a Stroke for this study?"
Heart failure requiring hospitalization	Positively adjudicated by CEC: Yes to the question "Does the event meet the definition of a Heart Failure Event for this study?"
Bone fractures	Positively adjudicated by CEC: Yes to the question "Did the Fracture occur?"
Diabetic ketoacidosis	Positively adjudicated by CEC: Yes to the question "Does this event meet the criteria to be a DKA event?"
EOSI Renal events where select events adjudicated	
Sustained ≥50% decrease in eGFR	(1) For ≥50% decrease in eGFR from baseline, (1a) confirmed ≥50% decrease in GFR for ≥30 days with no reversible cause as recorded in eCRF "eGFR decrease", OR (1b) positively adjudicated by CEC: Yes to the question "Does the subject meet the criteria of CKD progression".

Statistical Analysis Plan

Version: Final 3.0
Lexicon Pharmaceuticals Protocol No. EFC14837

Date of Issue: 21 November 2019
Covance Study ID:000000155205

AE Grouping	Criteria
Sustained eGFR <15 mL/min/1.73 m ²	(2) For eGFR <15 mL/min/1.73 m ² , (2a) confirmed eGFR <15 mL/min/1.73 m ² for ≥30 days with no reversible cause as recorded in eCRF "eGFR decrease", OR (2b) positively adjudicated by CEC: Yes to the question "Does the subject meet the criteria of CKD progression".
Chronic dialysis	(3) For dialysis, (3a) dialysis lasted for ≥90 days (eg, end date - start date+ 1 ≥90) as recorded in eCRF "Renal Event - Dialysis", OR (3b) positively adjudicated by CEC: Yes to the question ". Does the subject meet the criteria for ESRD".
Renal transplant ^a	(4) "Renal transplant" captured in eCRF "Other procedure form", where adjudication is not required. PTs of Renal transplant (10038533), Renal and pancreas transplant (10052278), Renal and liver transplant (10052279) based on MedDRA v21.1.
Renal death	(5) Renal death as positively adjudicated by CEC: "Death - Non-Cardiovascular (Renal)" as the primary cause of death
EOSI not adjudicated^a	
Severe hypoglycemia	Algorithm specified in Section 2.1.4.1 based on eCRF "Hypoglycemic Events"
Genital mycotic infections	PTs in Appendix C
Urinary tract infections	PTs in Appendix C
Clinically relevant volume depletion and events related/possibly related to volume depletion	PTs in Appendix C
Diarrhea	Narrow search on "Noninfectious diarrhoea (SMQ)" [20000218] plus the following PTs (MedDRA v21.1): Gastroenteritis (10017888), Antidiarrhoeal supportive care (10055660), Enteritis (10014866), Enteritis leukopenic (10014877), Enterocolitis (10014893), Enterocolitis haemorrhagic (10014896)
Pancreatitis	PTs in Appendix C
Venous thrombotic events	PTs in Appendix C
Malignancies of special interest	Breast cancer: Narrow search on "Breast neoplasms, malignant and unspecified (SMQ)" [20000149] Prostate cancer: Narrow search on "Prostate neoplasms, malignant and unspecified (SMQ)" [20000152] Leydig-cell cancer: PTs of Leydig cell tumour of the testis (10024407) and Ovarian Sertoli-Leydig cell tumour (10073270) based on MedDRA v21.1 Thyroid cancer: PTs in Appendix C Renal cell cancer: PTs in Appendix C Pancreatic cancer: PTs in Appendix C Bladder cancer: PTs in Appendix C
EOSI AE leading to an amputation	
AE leading to an amputation	"AE Correction" as the reason for amputation in eCRF "Other Procedures related to amputation"
AE potentially leading to an amputation ^{a,b}	PTs in Appendix C

AE Grouping	Criteria
a	Search terms will be updated using the MedDRA version currently in effect at Covance at the time of database lock for EOSI identified by them.
b	AE potentially leading to amputation: not one of EOSI defined in protocol, included and analyzed due to their relevance in regards to lower limb complications and amputations as a requirement from health authorities.

2.1.4.3 Deaths

The deaths observation period are per the observation periods defined above.

- Death on-study: deaths occurring during the on-study observation period.
- Death on-treatment: deaths occurring during the TEAE period.
- Death post-study: deaths occurring after the end of the study.

2.1.4.4 Laboratory safety variables

Clinical laboratory data consists of blood analysis (including hematology, clinical chemistry, amylase, lipase, and lipid profile) and urinalysis. Clinical laboratory values will be summarized in both standard international units and conventional units when applicable.

Blood samples for clinical laboratories will be taken at designated visits (see study flowchart in Appendix E). The following laboratory parameters will be assessed by central laboratory:

- Hematology
 - **Red blood cells and platelets:** hemoglobin, hematocrit, red blood cell count, platelet count,
 - **White blood cells:** white blood cell count, neutrophils, lymphocytes, monocytes, basophils, eosinophils.
- Clinical chemistry
 - **Metabolism:** glucose (serum), creatine phosphokinase (CPK),
 - **Electrolytes and minerals:** sodium, potassium, chloride, calcium, phosphorus, bicarbonate (ie, carbon dioxide), magnesium,
 - **Renal function:** creatinine, blood urea nitrogen (BUN), uric acid,
 - **Liver function:** total protein, albumin, alanine aminotransferase, aspartate aminotransferase, alkaline phosphatase, lactic acid dehydrogenase (LDH), total bilirubin.
- Lipid parameters (fasting)
 - Total cholesterol (TC),
 - High density lipoprotein cholesterol (HDL-C),
 - Low density lipoprotein cholesterol (LDL-C) (calculated by Friedwald equation),
 - Non-HDLC (calculated as the difference between TC and HDLC),
 - Triglycerides (TG).

- Pancreatic enzymes: lipase, amylase.
- Markers of intestinal transit and absorption
 - Vitamins: B6, B12, K, E and A,
 - Serum folate,
 - Ferritin.
- Markers of bone and calcium metabolism
 - Calcium,
 - 25-hydroxyvitamin D,
 - 1,25-dihydroxyvitamin D,
 - Phosphorus,
 - Parathyroid hormone (PTH),
 - Markers of bone resorption: N-terminal telopeptide (NTX), beta-C-terminal telopeptide (β -CTX-1),
 - Marker of bone formation: type 1 procollagen N-terminal (P1NP), osteocalcin.

Urine samples will be collected at designated visits (see study flowchart in Appendix E) and the following laboratory data will be measured at a central laboratory:

- Urine dipstick includes: specific gravity, pH, protein, blood, ketones, bilirubin, urobilinogen, nitrite, and leukocyte esterase.
- Urine microscopy includes, but is not limited to: detection of formed cellular elements, casts, bacteria, yeast, parasites, and crystals in centrifuged urine sediment.
- Urine albumin, calcium, phosphorus, glucose, magnesium, and creatinine.

Serum glucose, UGE, calculated UACR and calculated UGCR will be presented as efficacy parameters in [Section 2.4.4](#).

Technical formulas are described in [Section 2.5.1](#).

